**Document History Table**

DOCUMENT HISTORY			
Document	Version	Date	Comments (if applicable)
Amendment 3	4.0	02 OCT 2023	
Amendment 2	3.0	19 AUG 2022	
Amendment 1	2.0	17 SEP 2021	
Clinical Study Protocol	1.0	28 JUN 2021	Original version (internal use only)

**Amendment 3 (02 OCT 2023)****Overall Rationale for the Amendment:**

It was planned to enroll a maximum of 70 participants such that approximately 60 evaluable participants would complete the study. Due to the observed rate of recruitment, it will not be feasible to enroll 70 participants within the planned recruitment period. Given the actual recruitment (as of August 2023), it is assumed that only 20-25 participants will be enrolled by the end of 2023. The protocol was updated to describe the anticipated reduced sample size and the impact on the precision of estimates.

Furthermore, the inclusion criteria were adjusted to reduce restrictions to enrollment.

Although the change in inclusion criteria has the potential to introduce bias in comparisons to patients enrolled prior to the amendment, the risk is thought to be minimal given the 2 possible extreme scenarios below:

- o 1 – interruptions in treatment (eg, insurance, migration): a maximum period of 6 months (assuming untreated during that time) is not expected to dramatically change patients' disease phenotype such that it would reflect during Jivi prophylaxis while on study
- o 2 – patients treated with an extended half-life (EHL) prior to study entry: the reason for switching to an EHL following stable SHL prophylaxis could be due to external conditions unrelated to patients' bleeding phenotype (eg, formulary changes, insurance requirements, patient preference, etc.). Nevertheless, if the change to an EHL treatment was due to a patient's bleeding phenotype and/or any structural differences compared to any patients enrolled before amendment 3, the risk of bias is thought to be low, since any data from the time of EHL treatment are excluded from the risk score calculation for those patients remaining to be enrolled.

Due to the decision to no longer pursue enrolling participants from Colombia, the protocol is amended back to a single country United States study.

The changes incorporated in this amendment are described in the table below. Edits to update amendment number and dates in the current version, and minor editorial changes for style have been made, but are not documented in the table.

Section # and Name	Description of Change	Brief Rationale
1.1 Synopsis, Overall Design 1.1 Synopsis, Number of Participants	Changed number of participants approximately assigned to study intervention from 70 to 20-25	Due to feasibility reasons, specifically the observed rate of recruitment
	Added definition for determination of pre-study annualized bleed (ABR), treatment frequency, and stable standard half-life (SHL) prophylaxis.	Clarification of terms used in protocol, and removal of reference to multi-country study design

	Removed "multi-country"	
Section 1.2 Figure 1-1: Dosing Regimen Schema	Updated N and clarified trough level timepoint at Month 3	Updated due to reduction of study sample size and for clarification
Section 1.3 Schedule of Activities (SoA)	
Human coagulation factor VIII (FVIII) levels line item: added note describing required washout period for patients whose previous product was an SHL or extended half-life (EHL). Added a conditional measurement timepoint in Visit 5 and Visit 6 columns and new footnote g in Visit 2, Visit 5, and Visit 6 columns
 
Web-Accessible Population Pharmacokinetic Service-Hemophilia (WAPPS-Hemo) analysis line item: added note describing use of FVIII levels from Visit 2 and Visit 5, and a reference to footnote h
 
FVIII trough levels line item: added a note clarifying that Visit 5 level will be first of 2 trough levels for those on a 2x/week regimen
 
Created new footnote g; subsequent footnotes renumbered
 
Updated footnote h to clarify timepoints for WAPPS-Hemo data entry
 
Clarified footnote j regarding timing of trough level measurements
	
Clarification of washout period and addition of a conditional measurement timepoint
 
Clarification of which FVIII levels to use in WAPPS-Hemo
 
Clarification; text moved from footnote to table
 
Creation of footnote describing conditional timepoint for repeating FVIII levels
 
Clarification
 
Clarification

Section 2.1 Study Rationale; Section 4.1 Overall Design;	Added definition for determination of pre-study ABR, treatment frequency, and stable SHL prophylaxis	
Clarification of terms used throughout protocol
 
The rationale to continue with the current baseline definition is that a comparison between SHL and score-based Jivi prophylaxis is intended, and inclusion of another period (untreated or different treatment) would bias this comparison.

Section 4.1 Overall Design; Section 9.4.1 General Considerations; Section 9.4.5.1 Disposition of Participants	Removed text identifying the study as a multi-country design, text stating that primary endpoint tables will be stratified by country to consider a potential country effect, and text stating that disposition will be presented by country	Due to decision to no longer pursue enrolling participants from Colombia
Section 4.1 Overall Design	Added Screening schematic to clarify screening process (Figure 4-1); updated subsequent figure numbering	Clarification
	Text describing possible interim analysis removed due to reduction in study sample size	Due to reduction in sample size
	Text describing rationale for the baseline definition, and statement regarding feasibility of drawing conclusions with reduced sample size added	Clarification
	Cross-reference to Section 9.4.2	Clarification and improvement of

	added for full definition of pre-study ABR, treatment frequency, and stable SHL prophylaxis	document navigation
Section 4.1, Table 4-1: Parameters for determining participant risk scores	Participant Variables were clarified. New footnotes a and b were added and subsequent footnotes renumbered accordingly	Clarification
Section 4.1.1 Screening	Text clarified to read that during the screening period, participants will continue treatment with their current FVIII treatment	Clarification
Section 5 Study Population	Text added to allow that adolescent/adult participants must be previously treated, and on continuous prophylaxis with an SHL FVIII product for at least 6 consecutive months within the previous 12 months prior to the screening visit	Adjustment of requirements for participants
Section 5.1 Inclusion Criteria; Inclusion Criterion #3	Text added to modify requirements and window for prophylaxis with SHL FVIII with a stable frequency prior to start of study intervention, to define stable frequency, and to permit non-Jivi EHL between the 6-month stable SHL prophylaxis period and start of study treatment	Adjustment to reduce restrictions to enrollment
Section 5.1 Inclusion Criteria; Inclusion Criterion #4	Text added to clarify requirements and to clarify that window for evaluating documented bleeding rate (ABR) occurs prior to screening	Clarification
Section 5.1 Inclusion Criteria; Inclusion Criterion #5	Text added to modify conditions under which a participant can be enrolled if they had past evidence of a positive inhibitor titer	To relax restrictions to enrollment due to lack of evidence of past FVIII inhibitors presenting an issue in patients with subsequent negative titers for inhibitors
Section 5.2 Exclusion Criteria; Exclusion Criterion #3	Reduced evidence of inhibitor to FVIII from 3 years to 1 year	Alignment with Inclusion Criterion #5
Section 5.2 Exclusion Criteria; Exclusion Criterion #6	Added cross-reference to Inclusion Criterion #4 and Section 9.4.2	Clarification and cross-reference to full definition for improved document navigation
Section 6.3 Measures to Minimize Bias: Randomization and Blinding	Text added to describe potential for introduction of bias due to pre-study window of bleed frequency data collection	Transparency about possible introduction of bias due to change in data collection time period
Section 8.1.1 Demographics	Removed country from demographic characteristics to be recorded at screening	Due to decision to no longer pursue enrolling participants from Colombia
Section 8.1.3 Disease History	Clarification of information on history of hemophilia to be recorded at screening	Clarification
Section 8.2 Effectiveness Assessment	Note added with cross-references to the sections of the protocol with full definitions of pre-study ABR, treatment frequency, and stable SHL prophylaxis	Clarification and improvement of document navigation
Section 8.2.1 Treatment Logs/Bleeding Verification	Corrected that participants and their parent or legal guardian will be trained on the use of eDiary at the Baseline Visit rather than the screening visit	Corrected to align with SoA
Section 8.2.3 Joint status assessment	Corrected that joint status assessment will occur at baseline	Correction

	rather than at screening	
Section 8.4.1 Time Period and Frequency for Collecting AE and SAE Information	Text added to clarify that bleeds that occur during the screening period should be recorded in the participant's medical record	Clarification
Section 9.2 Sample Size Determination	Anticipated sample size changed from 70 to 20-25. Precision of estimates for the primary outcome updated accordingly. Statement regarding low expected precision added  Table 9-1 replaced with table presenting updated estimates appropriate for reduction in sample size  Statement regarding feasibility of drawing conclusions with reduced sample size added	Due to feasibility reasons. To be transparent about estimate precision for reduced study size
Section 9.4.2 Primary Endpoints	Text added to comprehensively define the basis for establishing pre-study ABR and treatment frequency, and stable SHL prophylaxis	Clarification
	Removed text stating that outcome on risk score-selected prophylaxis regimen will be presented by country	Due to decision to no longer pursue enrolling participants from Colombia
Section 9.4.3 Secondary Endpoints	Added cross-reference to Section 9.4.2 for definition of pre-study values	Clarification of terms and improvement of document navigation
Section 9.5 Interim Analysis	Text was changed to Not applicable, as due to reduction in sample size for the study, no interim analysis will be performed	Due to change in study sample size
Appendix 7 Section 11.7.4 Visit 5 – (Month 3) and Section 11.7.5 Visit 6 – (Month 6, End of Study/Early Withdrawal)	Text added regarding a conditional measurement timepoint, to align with new footnote g in Visit 5 and Visit 6 columns of the SoA	Consistency and addition of a conditional measurement timepoint
Appendix 10, Section 11.10 Definitions (Common Terms)	Added definitions for Pre-study ABR, Pre-study Treatment Frequency, and Stable SHL prophylaxis	Clarification of common terms used throughout the protocol
Section 11.3 Appendix 3, Clinical Laboratory Tests	Referenced table number corrected from 10-1 to 11-1	Correction
Section 11.7.1 Visit 1-Screening (Up to 30 Days Prior to Baseline)	Corrected table number referenced for blood sample information from 10-1 to 11-1	Correction

**Protocol Date:** 02 OCT 2023

Name: PPD PPD

Role: PPD

This is an electronically generated document that does not bear any sponsor signatures. The signature of the sponsor's medically responsible person is filed in the Trial Master File (TMF) and available on request.

Medical Monitor (Study Medical Expert) name and contact information can be found in the TMF.

## 1. Protocol Summary

### 1.1 Synopsis

**Protocol Title:** A multicenter, prospective, open-label clinical study to assess the effect of using a new risk score approach to select the most appropriate prophylaxis regimen for reaching a favorable outcome, when hemophilia A patients switch from standard half-life products to danoctocog alfa pegol (Jivi)

**Brief Title:** Jivi interventional study to assess a new risk score approach

**Rationale:** This study aims to assess a new risk score approach utilizing the best known phenotypic and biologic variables to select the most appropriate prophylaxis regimen for reaching a favorable outcome when switching from standard half-life (SHL) human coagulation factor VIII (FVIII) treatment to Jivi.

### Objectives and Endpoints:

Objectives	Endpoints
Primary	
To assess the effect of using a baseline risk score, based on a participant's phenotypic and biologic variables, to select the most appropriate prophylaxis regimen for reaching a favorable outcome, when switching from a SHL product to Jivi	Occurrence of favorable outcome on the score selected dosing regimen
Secondary	
To assess the effectiveness of Jivi compared to a previous SHL treatment	ABR (total, joint, spontaneous) and change in total ABR from pre-study
To assess the frequency of Jivi administration	Change in the frequency of pre-study SHL treatment to the frequency of Jivi administration (infusions/month)
To assess the proportion of participants with 0 and $\leq 1$ spontaneous bleeds	Occurrence of participants with 0 and $\leq 1$ spontaneous bleeds
To assess participant quality of life (QoL) and physical activity, as measured by Patient Reported Outcomes (PROs)	Change in Haemophilia Quality of Life Questionnaire (Haem-A-QoL or Haemo-QoL); Patient's Global Impression of Change (PGI-C); EuroQoL 5 Dimensions (EQ-5D-5L) questionnaire; Treatment Satisfaction Questionnaire for Medication (TSQM); Work Productivity and Activity Impairment (WPAI) questionnaire scores
To assess target joint status, per International Society on Thrombosis and Haemostasis (ISTH) guidelines	Number of target joints and change in target joint status from baseline

Other, Pre-specified	
To assess whether blood type and body mass index (BMI) would have led to a different score allocation	Participant score considering ABO type and BMI
To describe pharmacokinetic (PK) parameters derived from Web-Accessible Population Pharmacokinetic Service-Hemophilia (WAPPS-Hemo) and assess an association with clinical risk score	PK parameters derived from WAPPS-Hemo
To determine participant Jivi trough levels while on a specific regimen	Trough measurement of Jivi levels
To determine the percentage of participants who can maintain > 1%, > 3 %, and > 5% FVIII trough levels while on a specific prophylaxis regimen	Occurrence of trough levels above 1%, 3% and 5%, stratified by prophylaxis regimen
Abbreviations: ABR = annualized bleeding rate; EQ-5D-5L = EuroQoL 5 dimensions; FVIII = human coagulation factor VIII; SHL = standard half-life	

### Overall Design:

This is a multicenter, open-label, single arm, prospective study of previously-treated adolescent/adult ( $\geq 12$  years) patients (PTPs) with congenital hemophilia A treated with a SHL FVIII product for regular prophylaxis who are willing to switch to the extended half-life (EHL) product, Jivi (throughout this document, the symbol ® indicating a proprietary name is not displayed for Jivi. However, the omission of the symbol does not imply that this name is not protected). The study will be conducted to assess the effect of using a new risk score approach to select the most appropriate prophylaxis regimen for reaching a favorable outcome. Favorable outcome is defined for this study as: no dosing regimen change from the risk score-assigned regimen during the study period along with an improved annualized bleeding rate (ABR) from pre-study ABR and decreased or similar dosing frequency compared to the previous treatment, or no dosing regimen change compared to risk score-assigned regimen with a similar ABR and a decreased dosing frequency compared to the previous treatment. All participants will have received prophylaxis with any licensed SHL FVIII product with a stable dosing regimen. Pre-study ABR and treatment frequency is based on data from a minimum of 6 continuous months (up to a maximum of 12 months) of stable SHL prophylaxis at any given time within the 12 months prior to the screening visit. Stable SHL prophylaxis is defined as a minimum of 18 weeks of treatment in a 6 (consecutive) calendar month period in the 12 months prior to the screening visit.

At baseline, participants' total risk scores will be determined based on 5 individually weighted variables: pre-study bleeding phenotype, number of active target joints, von Willebrand factor (vWF) antigen levels, previous treatment frequency, and physical activity. All parameters are determined at screening. If the physical activity variable is missing, then zero will be assigned. When other variables are missing, the participant score cannot be determined and participant data cannot be analyzed. The total risk score is used to assign participants to 1 of 3 prophylaxis regimens according to their score. The effect of participants' risk scores on determining the most appropriate prophylaxis regimen will be evaluated by the proportion of participants with a favorable outcome.

Along with regimen details and ABR, data collected will include PRO measurements (Haemophilia Quality of Life Questionnaire [Haem-A-QoL or Haemo-QoL], Patient's Global Impression of Change [PGI-C], EuroQoL 5 Dimensions [EQ-5D-5L], Treatment Satisfaction Questionnaire for Medication [TSQM], and Work Productivity and Activity Impairment [WPAI] questionnaires), joint status outcomes, human recombinant factor VIII (rFVIII) incremental recovery and trough levels, and safety including treatment-emergent adverse events (AEs). Additional data will include documentation of blood type and BMI, and a Web-Accessible Population Pharmacokinetic Service-Hemophilia (WAPPS-Hemo) pharmacokinetic (PK) analysis to determine whether these would have contributed to another risk score assignment for the prophylaxis regimen.

**Intervention Model:** Single group

**Primary Purpose:** Assess the effect of using a new risk score approach to select the most appropriate prophylaxis regimen

**Number of Arms:** One treatment arm with 3 different regimens

**Masking:** No masking

**Brief Summary:**

The purpose of this study is to assess the effect of a new risk score approach based on participant's phenotypic and biologic variables to determine the most appropriate prophylaxis regimen for adolescent/adult ( $\geq 12$  years) PTPs with congenital hemophilia A who switch from a SHL FVIII prophylaxis to an EHL product (Jivi).

**Study Duration:** Approximately 7.5 months

**Treatment Duration:** 6 months

**Number of Participants:** Approximately 20 – 25 participants will be assigned to study intervention.

**Intervention Groups and Duration:**

All eligible participants will be assigned a risk score at baseline and will start treatment 2x/week (40 IU/kg/dose) with Jivi for 4 weeks. Treatment will then continue based on their assignment to 1 of the 3 following prophylaxis regimens:

- Participants with a high risk score ( $> 4$ ) continue on prophylaxis 2x/week (40 IU/kg/dose)
- Participants with a medium risk score (2 to 4) will switch after 4 weeks to prophylaxis Q5D (50 IU/kg/dose)
- Participants with a low risk score ( $< 2$ ) will switch after 4 weeks to prophylaxis Q5D (50 IU/kg/dose) and then after 4 weeks to a less frequent (e.g. Q7D) regimen (60 IU/kg/dose)

Prophylaxis regimens will not be altered during the study period unless a participant experiences  $\geq 2$  muscle or joint bleeds (without evident trauma) during any given 8-week period during the 6-month study. These participants will be assigned to the next highest dosing frequency. In line with the Jivi prescribing information, the treating investigator reserves the right to change a participant's regimen at any time if the investigator determines the score-determined regimen is not well-suited for the participant.

The participants' planned study duration, including a screening (up to 30 days), treatment (6 months), and safety follow-up period (14 days after last dose), will be approximately 7.5 months.

The details regarding duration and risk score assigned prophylaxis regimen are as follows:

[figure not shown]

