## 1.2 Schema for Dosing Regimen Assignment

**Figure 1–1: Dosing Regimen Schema**

Abbreviations: PK = pharmacokinetics; Q5D = every 5 days; Q7D = every 7 days; SHL = standard half-life; vWF = von Willebrand factor.

a Score exception: if  $\geq 2$  muscle or joint bleeds (without evident trauma) occur within any given 8-week period during the 6-month study, then the protocol recommends assigning the participant to the next highest frequency regimen. Per protocol, the treating investigator reserves the right to change a participant's regimen at any time if they perceive the risk score-determined regimen is not well-suited for the participant.

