**Table 4-3: Dosing Regimens**

Procedure	Duration	Dose regimen	
Screening	Up to 30 days prior to Baseline	Continuation of previous treatment	
	Week 1-4	Starting dose 40 IU/kg/dose 2x/week	
Treatment Phase	Week 5-8	Low Risk	Switch to 50 IU/kg/dose Q5D until Week 8
		Medium Risk	Switch to 50 IU/kg/dose Q5D until end of study
		High Risk	Continue 40 IU/kg/dose 2x/week until end of study
	Week 9	Low Risk	Switch to less frequent dosing 60 IU/kg/dose (e.g. Q7D) a until end of study

Abbreviations: CRF = case report form; Q5D = every 5 days; Q7D = every 7 days.

a As determined by the investigator.

Note: For twice weekly dosing regimens, dosing must be administered at 3- and 4-day intervals. If a dose is missed, it will be documented in the CRF and the next dose will be administered as soon as possible before resuming the regular schedule.

Note: If  $\geq 2$  muscle or joint bleeds (without evident trauma) occur within any given 8-week- period during the 6-month study, then the participant will be assigned to next highest frequency regimen. Per protocol, the treating investigator reserves the right to change a participant's regimen at any time if the treating investigator determines the score-determined regimen is not well-suited for the participant.

Participants are allowed to change the dose frequency at any time during the study in case of increase in bleeding frequency as per investigator judgment. The recommended maximum total dose per infusion should not be higher than 6000 IU.

Participants who have an unplanned major surgery will be treated at the discretion of the investigator per their standard of care. Treatment with other FVIII products after unplanned major surgery is also acceptable according to local practice at the discretion of investigators. Participants will resume their prophylaxis regimen with Jivi as per protocol after recovery.

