## **6.5 Dose Modification**

If a participant treated with an extended interval regimen experiences  $\geq 2$  muscle or joint bleeds (without evident trauma) within any given 8-week period during the study, then he/she will be assigned to next highest frequency regimen. In line with the Jivi prescribing information, the treating investigator reserves the right to change a participant's regimen at any time if he/she determines the score-determined regimen is not well-suited for the participant.

Further dose adaptations according to participant needs and at the investigator's discretion are allowed within the approved dose range and rounding up to full vials which may result in slightly higher dosages.

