#### Definitions

- No regimen change during study: participant is treated according to the score-assigned regimen and does not deviate or switch frequency.
- Improved ABR: Reduction from pre-study ABR is  $\geq 1$ .
- Similar ABR: Absolute change from pre-study ABR is  $< 1$ .

- Worse ABR: Increase from pre-study ABR is  $\geq 1$ .
- Decreased frequency of administration: Reduction from pre-study in number of infusions per month is  $\geq 2$ .
- Similar frequency of administration: Absolute change from pre-study in number of infusions per month  $< 2$ .
- Worse frequency of administration: Increase from pre-study in number of infusions per month is  $\geq 2$ .

Pre-study ABR and treatment frequency is based on data from a minimum of 6 continuous months (up to a maximum of 12 months) of stable SHL prophylaxis at any given time within the 12 months prior to screening. Stable SHL prophylaxis is defined as a minimum of 18 weeks of treatment in a 6 (consecutive) calendar month period in the 12 months prior to the screening visit.

A switch to a higher frequency regimen due to a bleed during study is considered as non-favorable outcome, whereas participants who switch due to other reasons (e.g. personal decision, study compliance issues, or changes in physical activity level) will be censored at time of switch.

The number (frequency) of participants switching the risk score-selected dosing regimen will be summarized.

As sensitivity analyses, the proportion of participants with favorable outcome on the risk score-selected prophylaxis regimen will be presented by inhibitor history.

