### 4.2.2 Main Analytical Approach

The analysis of the primary endpoint will be performed on the mITT population.

The entire study intervention period will be analyzed regardless of the score assigned dosing regimen (i.e. during the first 8 weeks on the study).

The strategy for primary endpoint analysis, including how to deal with participants who switch regimen frequency is listed below:

- A switch to a higher frequency regimen than the one assigned by the score, due to a bleed during study, is considered as non-favorable outcome
- Participants who switch due to other reasons than bleeding events (e.g. personal decision, study compliance issues, or changes in physical activity level) will be censored at the time of regimen change
  - switch after 4 months ( $> 122$  days): participant data will be analyzed until censoring
  - switch prior to 4 months ( $\leq 122$  days): participant data will not be used for analysis, as it is assumed that a shorter duration will not be sufficient to correctly estimate the ABR and would bias the results.

Note: a decrease in regimen per score assignment (during the first 8 weeks) is not considered a switch as discussed above.

Favorable outcome assessed by total ABR and frequency of administration (/month) is evaluated after considering regimen switch events.

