#### **4.2.3 Sensitivity Analysis**

The following analysis will be performed if numbers of participants in the mITT population with and without history of FVIII inhibitors are each  $\geq 5$ : As sensitivity analyses, the proportion of participants with favorable outcome on the risk score-selected prophylaxis regimen will be presented by inhibitor history.

The following analysis will be performed if  $> 3$  participants in the safety analysis set are excluded from the mITT: The proportion of participants with favorable outcome will be reported for the safety analysis set, assigning non-favorable outcome to participants who discontinued or switched regimen prior to 4 months.

A further sensitivity will be conducted, assigning non-favorable outcome to all participants who discontinued or switched regimen at any time during study.

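### A participant who meets the 8-week bleed criterion but is not stepped up can still count as favorable, and two figure footnotes word the step-up only as a recommendation

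*Protocol*

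**What the plan says.** **The step-up rule.** The mandatory wording appears in four places. The synopsis text on intervention groups says "These participants will be assigned to the next highest dosing frequency". The note under the synopsis dosing table says the same in substance. The note to protocol Table 4-3 says "then the participant will be assigned to next highest frequency regimen". Protocol Section 6.5 (Dose Modification) is also mandatory and is the only place that limits the rule to extended intervals: "If a participant treated with an extended interval regimen experiences" the qualifying bleeds. The footnote to protocol Figure 1-1 is weaker: "then the protocol recommends assigning the participant to the next highest frequency regimen". The footnote to SAP Figure 1 repeats that wording.

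**The endpoint.** Favorable outcome needs no change from the score-assigned regimen plus a qualifying combination of ABR and infusion frequency against pre-study values. Protocol 9.4.2 defines no regimen change as "participant is treated according to the score-assigned regimen and does not deviate or switch frequency". It then says "A switch to a higher frequency regimen due to a bleed during study is considered as non-favorable outcome". SAP 4.2.2 keeps this: a move above the assigned frequency "due to a bleed during study, is considered as non-favorable outcome".

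**The sensitivity analyses.** SAP 4.2.3 splits by inhibitor history, reassigns participants who discontinued or switched before 4 months, and adds a version "assigning non-favorable outcome to all participants who discontinued or switched regimen at any time during study". All the reassignments act on participants who left the study or the regimen.

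**The concern.** The 8-week criterion is the protocol's own signal that an extended interval may be too long for a participant. The endpoint does not use that signal directly. It uses the dosing decision that should follow. Someone who meets the criterion and stays on the assigned regimen has, on the wording of 9.4.2, neither deviated from that regimen nor switched frequency, and is judged on ABR and frequency alone. Someone with the same bleeds who is stepped up is non-favorable by rule.

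For such participants the primary outcome depends partly on an open-label decision by the site. The effect runs one way: an unswitched case can only raise the favorable proportion. The footnotes matter because a site that did not step a participant up could cite them to argue that no deviation occurred.

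**Working it through.** **1. Reproduce the plan's figures.** The exact Clopper-Pearson interval for 14/20 is 45.7% to 88.1% (width 42.4), as in protocol Table 9-1. The SAP 4.1.1.4 examples also reproduce: 30.4375 × 52 / 182 = 8.6964 and 30.4375 × 32 / 182 = 5.3516 infusions per month.

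**2. Is frequency decreased on an extended interval?** SAP 4.1.1.4 uses the prescribed schedule, and decreased means a reduction of at least 2 per month. Over 182 days:
- Q5D: 8 doses in the first 28 days, then 31, giving 39 doses; 30.4375 × 39 / 182 = 6.52 per month.
- Q7D: 8 + 6 + 18 = 32 doses; 5.35 per month.

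| Pre-study regimen | Per month | Change on Q5D | Change on Q7D |
|---|---|---|---|
| 2x/week | 8.70 | −2.18 | −3.35 |
| 3x/week | 13.04 | −6.52 | −7.69 |

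All four are decreased. Under SAP 4.2.1 the participant then needs only an ABR change below +1.

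**3. Which pre-study ABR passes?** On-study ABR = 365.25 × bleeds / days (SAP 4.1.1.1). The table assumes that the bleeds shown are the only counted bleeds.

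| Bleeds, days | On-study ABR | Favorable if frequency decreased | Favorable if frequency similar |
|---|---|---|---|
| 2, 182 | 4.01 | pre-study ABR > 3.01 | pre-study ABR ≥ 5.01 |
| 2, 196 | 3.73 | > 2.73 | ≥ 4.73 |
| 3, 182 | 6.02 | > 5.02 | ≥ 7.02 |

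Day 196 is Day 182 plus the 14-day window for Visit 6.

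**4. A matched pair.** Both participants have pre-study ABR 4.0, 3x/week, no target joint, vWF below 100% and a sedentary lifestyle. The score is 2 + 0 − 1 + 2 + 0 = 3, so both are assigned Q5D. Each has two spontaneous joint bleeds 40 days apart while on Q5D, and no others.
- Stepped up for the bleeds: non-favorable by rule.
- Left on Q5D to Day 182: ABR change 4.01 − 4.00 = 0.01 (similar), frequency change −6.52 (decreased), so favorable.

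**5. Can such participants be on extended intervals?** Protocol Table 4-1 has 3 × 4 × 3 × 3 = 108 combinations of the other four variables for each ABR category. With ABR above 1 and up to 4, 29 are low and 56 medium (85 of 108). With ABR above 4, 14 are low and 54 medium (68 of 108). These are score combinations, not expected shares of participants.

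**6. Effect per case.** The number of cases is an assumption, shown as 0 to 3. The starting points are the Table 9-1 rows for an assumed true proportion of 70%.

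| Cases counted as non-favorable | N=20 | N=25 |
|---|---|---|
| 0 | 14/20 = 70% [45.7; 88.1] | 17/25 = 68% [46.5; 85.1] |
| 1 | 13/20 = 65% [40.8; 84.6] | 16/25 = 64% [42.5; 82.0] |
| 2 | 12/20 = 60% [36.1; 80.9] | 15/25 = 60% [38.7; 78.9] |
| 3 | 11/20 = 55% [31.5; 76.9] | 14/25 = 56% [34.9; 75.6] |

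**The case against.** **The switch is mandatory.** A reader might infer that the footnotes make it optional. The documents do not support that. Four statements, including the section that governs dose changes, require the step-up, and protocol Section 8 allows no waivers. A figure footnote does not override them. When there is time to act, leaving a criterion-meeter in place is a protocol deviation. What stands is narrower: the footnotes are inconsistent with the operative text and should match it. A participant who meets the criterion shortly before Month 6 may also go unswitched without any fault.

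**The cases may be found anyway.** A reader might also infer that no planned output would show them. That cannot be confirmed. The SAP introduction places table and listing specifications in a separate document, SAP 4.6.1 classifies deviations under a plan that was not available, and SAP Section 3 provides for a data review with documented deviations and validity findings. With 20 to 25 participants, the listings read against the switch table in SAP 4.6.3 would identify them. What can be said is that the SAP text specifies neither a count of these participants nor a re-estimate of the primary proportion.

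**The criterion is a dosing trigger, not an outcome.** This is fair. The endpoint compares each participant with their own past. Someone with pre-study ABR 6 and two bleeds on study (4.01) has improved by 1.99. That is a reason to leave the primary definition alone and use a sensitivity analysis.

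**Little depends on it.** The study tests no hypothesis, and both documents say that conclusions may not be possible. One case moves the estimate 5 points inside a 42.4-point interval. That keeps the point minor. However, the interval describes sampling error and does not cover a classification that depends on a site decision.

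**Conclusion.** The point holds as a minor one. The rule is worded inconsistently, and because the endpoint fails the switch rather than the criterion, two participants with the same bleeds can receive opposite primary outcomes. The divergence is conditional. With two counted bleeds at Day 182 and decreased frequency, it needs a pre-study ABR above 3.01. Below that, the unswitched participant is non-favorable anyway.

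Each case is worth 5 points at N=20 and 4 points at N=25, always upward. A reader might want an expected shift for the study. The documents give neither on-study bleed rates nor the chance that a required step-up is not made, so any such figure would mostly reflect assumed inputs. The number of cases may be zero.

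**What to change.** 1. **Wording.** In the footnotes to protocol Figure 1-1 and SAP Figure 1, replace the recommendation with the mandatory assignment, limited to extended-interval regimens as in Section 6.5. Change the SAP footnote in the SAP. Hold the protocol footnote for the next amendment, since an amendment needs IRB approval. By the protocol's own projection enrollment would end with 2023, so this edit may affect few dosing decisions.

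2. **Analysis, before database lock.** Add to SAP 4.2.3:
   - a count of extended-interval participants with at least two spontaneous joint or muscle bleeds within 56 days, after the 24-hour and 72-hour rules, who were not switched. Both bleeds must fall after the extended-interval regimen began, because everyone is on 2x/week for the first 4 weeks;
   - one sensitivity analysis of the primary endpoint that counts these participants as non-favorable;
   - a separate line for those who first meet the criterion in the last 30 days, when there is little time to act.

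The primary definition and the clinical criterion do not change. The eDiary already records bleed type, location and time, so no new data or visits are needed. The cost is one extra table and a sensitivity proportion that may be slightly lower than the primary one. If there are no cases, the table shows zero and supports the primary result.
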